10.1.1 Pharmacokinetic endpoints

The kinetics of single dose administration as well as multiple dose assessment will be evaluated.

Beyond the respective rhNGF plasma levels for both ELISA methods, the following parameters will only be investigated for each ELISA method, if the data warrant to do so:

- maximum observed serum concentration (C_{max}), time to reach C_{max} (t_{max}), time elapsed between dosing and the first serum concentration that exceeds the assay quantification limit (t_{lag}) as measured without treatment based on assessments on D-1
- C_{max} , t_{max} , t_{lag} of single dose regimen based on assessments on D1 and pre-dose of D2
- C_{max} , t_{max} , t_{lag} of multiple dose regimen based on assessments starting with pre-dose of D2
- serum concentration measured before the administration of the next dose (C_{trough}) as assessed at pre-dose visit on D2, D3, D4, D5, D6
- $AUC_{[0-24]}$ for the single dose regimen and the first day of multiple dose regimen. $AUC_{[0-24]}$ as area under the serum concentration versus time curve from time 0 h to pre-dose value of the next day calculated by the linear trapezoidal rule. Values below the level of quantitation will be set to 0. Values below the baseline concentration will be set to zero other than for the values for which no later values above the baseline concentration are available, which will be set to missing.
- $AUC_{0-t_{last}}$ for the multiple dose regimen. This is derived as area under the serum concentration versus time curve from time 0 h to the last data point t_{last} after drug administration above the limit of quantitation and the baseline concentration, calculated by the linear trapezoidal rule.

Values below the baseline concentration will be set to zero other than for the values for which no later values above the baseline concentration are available, which will be set to missing

- AUC for the multiple dose regimen. AUC will be derived as area under the serum concentration versus time curve extrapolated to infinity, calculated as $AUC = AUC_{0-t_{last}} + C_{last}/\lambda_z$

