- *maximum observed serum concentration (C_{max}), time to reach C_{max} (t_{max}), time elapsed between dosing and the first serum concentration that exceeds the assay quantification limit (t_{lag}) as measured without treatment based on assessments on D-1*
- *C_{max} , t_{max} , t_{lag} of single dose regimen based on assessments on D1 and pre-dose of D2*
- *C_{max} , t_{max} , t_{lag} of multiple dose regimen based on assessments atating with pre-dose of D2*
- *serum concentration measured before the administration of the next dose (C_{trough}) as assessed at pre-dose visit on D2, D3, D4, D5, D6*
- *$AUC_{[0-24]}$ for the single dose regimen and the first day of multiple dose regimen. $AUC_{[0-24]}$ as area under the serum concentration versus time curve from time 0 h to pre-dose value of the next day calculated by the linear trapezoidal rule. Values below the level of quantitation will be set to 0. Values below the baseline concentration will be set to zero other than for the values for which no later values above the baseline concentration are available, which will be set to missing.*
- *$AUC_{0-t_{last}}$ for the multiple dose regimen. This is derived as area under the serum concentration versus time curve from time 0 h to the last data point t_{last} after drug administration above the limit of quantitation and the baseline concentration, calculated by the linear trapezoidal rule.*

Values below the baseline concentration will be set to zero other than for the values for which no later values above the baseline concentration are available, which will be set to missing

- *AUC for the multiple dose regimen. AUC will be derived as area under the serum concentration versus time curve extrapolated to infinity, calculated as $AUC = AUC_{0-t_{last}} + C_{last}/\lambda_z$*

The kinetics of single dose administration as well as multiple dose assessment will be evaluated.

The analysis of pharmacokinetic parameters will be based on the difference between the measured rhNGF value after dosing and the value measured at the corresponding time on Day -1.

Values below the limit of quantitation and missing values will be labeled and accounted for accordingly during evaluation.

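### The multiple-dose AUC0-tlast and AUC to infinity join trough to trough across Days 4-5, so they understate exposure if the half-life is short; no Day 6 AUC[0-24] is defined

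*SAP*

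**What the plan says.** SAP 7.2.17 repeats the parameter list of Protocol 10.1.1. Both make the parameters conditional on the data being adequate for each ELISA.

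- **AUC0-tlast** is defined in the protocol "for the multiple dose regimen. This is derived as area under the serum concentration versus time curve". The SAP has the same rule: "This is derived as area under the serum concentration versus time curve from time 0 h to the last data point", which must lie "above the limit of quantitation and the baseline concentration, calculated by the linear trapezoidal rule". No day inside the regimen is excluded.
- **AUC to infinity** is AUC0-tlast plus Clast divided by the terminal rate constant.
- **AUC[0-24]** is defined only "for the single dose regimen and the first day of multiple dose regimen", that is, for Days 1 and 2.
- **Baseline.** Parameters are based on "the difference between the measured rhNGF value after dosing and the value measured at the corresponding time on Day -1". Values below baseline are set to zero, "other than for the values for which no later values above the baseline concentration are available, which will be set to missing".
- **Sampling.** Protocol 1.1, Protocol Appendix 3 and SAP 7.2.17 each give Day 4 and Day 5 a single pre-dose sample. Six drops are given on each of those days. Day 6 has 9 or 10 samples, depending on the list, and FU1 0 h follows.
- **Outputs.** SAP section 12 lists no AUC table. SAP 7.2.17 allows a PK appendix if one is needed, to be finalised before unmasking; section 13 currently lists no appendix.

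**The concern.** A trapezoidal area is only as good as the sampling between its end points. Over Days 4 and 5 the only values are pre-dose ones, taken 14 h after the last drop of the day before. A straight line between such values passes under every peak on those two days. The extrapolation term cannot repair this, because it adds area only after tlast.

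Multiple-dose pharmacokinetics is part of the secondary objective. A figure reported as the AUC for the multiple dose regimen will be read as exposure over that regimen, and may be set beside other studies or populations. If the half-life is short, that figure would be too low. Meanwhile a late, well-sampled dosing day (Day 6) would have no exposure summary of its own.

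**Working it through.** **1. Reproduce the plan's sample count.** Appendix 3 PK times: Day -1 11, Day 1 11, Day 2 13, Day 3 6, Day 4 1, Day 5 1, Day 6 10, FU1 1, FU2 2, FU3 1. The sum is 57, and 57 x 5 mL = 285 mL, as in Protocol 8.11.1. The Protocol 1.1 list gives 54 (Day 2 has 11, Day 6 has 9). SAP 7.2.17 gives 58 (an extra Day 2 sample at 9 h). All three have one sample on Day 4 and one on Day 5.

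**2. Doses.** 5 days x 6 = 30 multiple-dose drops, as in SAP 7.2.4. Days 4-5 carry 12/30 = 40%.

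**3. What the rule does on Days 4-5.** Count time from the first Day 2 dose. The values from 48 to 96 h are the pre-dose values at 48, 72 and 96 h (the last is Day 6 pre-dose). The trapezoid is 12 x C48 + 24 x C72 + 12 x C96, or 48 x C for equal troughs C. If all three are zero, for example because they lie below their Day -1 values, these two days contribute nothing.

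**4. Size on Days 4-5.** Assumptions: one compartment, first-order absorption, no noise, no quantitation limit, terminal half-life 3 or 4 h (rat value, Protocol 2.3), ka 1-8 per h (assumed). Each dose adds ka/(ka-ke) x [exp(-ke t) - exp(-ka t)], with area 1/ke. A pre-dose value sums the six doses given 14, 16, 18, 20, 22 and 24 h earlier, plus carry-over; the exp(-ka t) terms are negligible by then.

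- *Half-life 4 h, ka 1.* ke = ln 2/4 = 0.1733. The sum of exp(-ke t) is 0.0884 + 0.0625 + 0.0442 + 0.0313 + 0.0221 + 0.0156 = 0.2641. Multiply by ka/(ka-ke) = 1.2096 and by carry-over 1/(1-2^-6) = 1.0159: C = 0.3245. Rule: 48 x 0.3245 = 15.6. True: 12/ke = 69.2. Captured: about 22%.
- *Half-life 3 h, ka 8.* ke = 0.2310. Sum 0.0997, times 1.0297, times 1.0039: C = 0.1031. Rule: 4.95. True: 51.9. Captured: about 10%.

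**5. Whole regimen.** Superpose all 30 doses, sample at the Appendix 3 times (dose-time samples taken pre-dose), and compare the trapezoid with 30/ke.

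| Absorption, half-life 3-4 h | Days 4-5 captured | Total captured |
|---|---|---|
| ka 1-8 per h | 10-22% | 57-69% |
| ka equal to ke (slow) | 36-56% | 75-83% |

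For ka 1-8 the total shortfall is 31-43%. Days 4-5 account for 0.40 x (1 - 0.22) = 0.31 to 0.40 x (1 - 0.10) = 0.36 of the true total, which is most of it.

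**6. Dependence on half-life.** A second run used the SAP times, absorption half-life 0.25-1 h and an assumed quantitation limit of 0-30% of peak, with lower values set to zero.

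| Half-life | AUC0-tlast as % of true area to tlast |
|---|---|
| 1 h | 42-57 |
| 3-4 h | 50-70 |
| 8 h | 73-84 |
| 12 h | 80-94 |
| 24-72 h | 89-110 |

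At 3-4 h, AUC to infinity was 52-70% of true. Values above 100% arise only when tlast is FU3, where one straight line spans 360 - 176 = 184 h (Appendix 3 total hours).

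**7. Day 6 alternative.** On the Appendix 3/SAP lists, the times common to Day 2 and Day 6 that also have a Day -1 match are 0, 4, 8, 10, 11, 12, 14, 16 and 24 h (the last being the next day's 0 h sample). A noise-free Day 6 AUC[0-24] on these recovers 84-101% of true at 3-4 h and 53-81% at 1 h. The Day 6/Day 2 ratio is within 1% of true at 3-4 h; the true ratio is itself only 1.02-1.06 (up to 1.21 with slow absorption). The Day 2 AUC on these times is 1-4% below the Day 2 AUC[0-24] of the plan at 3-4 h and 6-16% below at 1 h, because the 0.5 h and 2 h samples drop out.

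**The case against.** The best defence is that this figure may never be produced. The parameters are conditional, no AUC table is listed, and nothing is inferential. Protocol 2.6 reports detectable rhNGF in only 6 healthy volunteers, in a study that went up to 180 µg/mL against 20 µg/mL here. SAP 10.9 already summarises absolute and time-matched concentrations at every scheduled time, so Day 2 and Day 6 can be compared point by point. Pre-dose concentrations are a planned parameter, and compartmental analysis is allowed. The documents never use the term total exposure. The Day 6 AUC has weaknesses of its own if the half-life is near 1 h. All of this stands and limits the consequence. It does not make the rule sound in the case where it is used.

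Three stronger readings are tempting and not supported.

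- *The cumulative AUC is badly wrong whatever the half-life.* The documents give no human half-life. From about 24 h the error is roughly 10% either way. The statement in Protocol 2.6 that rhNGF did not accumulate, and the rat value, point to a short half-life but do not establish one.
- *Baseline subtraction and the follow-up samples inflate the AUC by a known amount.* That needs an endogenous level, an assay SD and a quantitation limit, none of which is given. The 32 and 15 pg/mL in SAP 7.2.17 are detection limits, and the rule "Values below the level of quantitation will be set to 0" stands only under AUC[0-24]. FU3 is 230 h after the last dose; at a half-life of 3-4 h a value above baseline there could only be noise or endogenous NGF.
- *Time 0 h is undefined.* The AUC0-tlast definition does not name it, but SAP 7.1 counts multiple-dose time from the first Day 2 dose, and Cmax is taken "of multiple dose regimen based on assessments atating with pre-dose of D2". Confirmation is enough.

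**Conclusion.** The point holds in a conditional form. If the parameters are derived, tlast is on Day 6 or later and the half-life is short, the stated rule understates drug exposure over the multiple-dose regimen, and AUC to infinity inherits the loss. The structural part rests on the documents alone: 12 of 30 doses fall on days with only a pre-dose sample. The size (57-69% captured, or 75-83% with slow absorption) is an illustration that rests on a rat half-life, an assumed absorption rate and no noise.

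The lack of a Day 6 AUC[0-24] is a gap that the scheduled samples can fill. The consequence is minor to moderate. It is worth correcting before unmasking, because the choice of exposure summary should not be made with results in view.

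**What to change.** In SAP 7.2.17 or its PK appendix, before unmasking, and applying only if parameters are derived:

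1. Add a Day 6 AUC[0-24], from Day 6 pre-dose to FU1 0 h, and a Day 6/Day 2 ratio computed on the common baseline-matched times, with one conditional table. State that the Day 2 AUC in the ratio differs slightly from the Day 2 AUC[0-24] already defined.
2. Label AUC0-tlast and AUC to infinity as sampled at trough only on Days 4-5 and not an estimate of total exposure. Alternatively, drop them and record the change in SAP 3.6.
3. Confirm that time 0 h is the first Day 2 dose, and state the latest sample that can be tlast, since SAP 7.2.17 lists FU3 with the multiple-dose samples.
4. Reconcile the Day 6 PK times: Protocol 1.1 stops at 12 h, while Appendix 3 and the SAP run to 16 h. On the Protocol 1.1 list the common matched times would be 0, 2, 4, 8, 10, 11, 12 and 24 h, which recover 97-108% of the Day 6 area at 3-4 h, with the ratio within 2%.

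Cost: SAP text, one conditional table, and a SAP 3.6 entry if the cumulative AUCs are dropped. No new samples are needed. Downsides: there is still no valid cumulative multi-day AUC, and the Day 6 level (though not the ratio) stays low, at about 53-81% of true, if the half-life is near 1 h.

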7.2.18 Immunogenicity Endpoints

ATA blood samples were taken on Baseline Visit 0 hr, and FU4 0hr.

The assessment times are documented on eCRF Pages “Pharmacokinetics – Anti-Therapeutic Antibodies”, the ATA levels will be provided as Excel files by external provider after the study has been unmasked for listing purposes.

8 Analysis Methods

8.1 General Methods

All endpoints of this study will be summarized using descriptive summary statistics, i.e. arithmetic mean, standard deviation (SD), minimum, median and maximum for quantitative variables by treatment group. If applicable, geometric mean together with 95% confidence interval and coefficient of variation will be reported for pharmacokinetic parameters. For qualitative variables, absolute and relative frequencies will be reported. Percentages will be based on the number of subjects in the respective treatment group.

For event-based variables (e.g. adverse events) the number of events as well as the incidences (i.e. number and percentage of affected subjects) will be provided.

Ocular assessments will be generally be presented separately by Study Eye and Non-Study Eye. All assessed data will be listed.

8.2 Specific Methods for Primary Safety and Tolerability Analyses

No inferential analyses are foreseen for this study. However, 95% confidence intervals for the geometric mean are calculated for pharmacokinetic analysis.

8.3 Statistical/Analytical Issues

8.3.1 Adjustments for Covariates

Not applicable as no inferential analyses are foreseen.

8.3.2 Handling of Dropouts or Missing Data

For the analysis, no imputation of data is planned; all data will be analysed as collected.

8.3.3 Data Review

In order to perform the statistical analysis of the final analysis, a decision needs to be made on evaluability of subjects and visits prior to locking the database and breaking the code for the masked study medication. In particular, a review of protocol deviations is required to evaluate the validity of planned analysis needs to be identified and corresponding actions needs to be defined, if any. This will be done at the Blind Data Review Meeting.

Performance of the Blind Data Review Meeting will require a clean database, i.e. all data are available including masked PK data of both assays, coded and no data queries are open.

No data entry should be performed between the data base Soft Lock and database lock. Exception would be Queries, which raised during the BDRM requiring a solution before data base Lock.

The scope of the BDRM will be:

- Evaluation of Re-Screened subjects
- Check correct assignment of allocated treatment and study eye
- Check protocol deviations and define analysis sets
- Review and confirmation of AESIs (sight threatening events)

More details on scope and performance of data review meetings will be described in a separate BDRM plan.

After the BDRM was performed, all decisions were summarized in BDRM Minutes, which were approved before the database was locked for the analysis.

8.3.4 Multicenter Studies

Not applicable since this is a monocentric study.

8.3.5 Multiplicity of Endpoints

Not applicable as not inferential statistics will be performed.

9 Interim Analyses

No interim analysis is planned for this study.

10 Overview of Tables, Listings and Figures

In this section, TLFs are presented content wise. The full set of TLFs are tabulated in section 12, where it will also be indicated whether the item is unique (or first mentioned) or a repeat. Mock shells for unique TLFs are presented in a separate document.

10.1 Disposition of Subjects

Based on the Total Set, a disposition summary of subjects includes the number (n) and percentage (%) of subjects in all analysis sets defined in Section 6.1. All percentages will be based on the number of subjects randomized. For the Total Set only the number of subjects will be presented.

The primary reason for study discontinuation will be summarized for the SAF providing counts (n) and percentages (%). This summary will also include counts and percentages for unmasked subjects.

A listing will be present for the Total Set displaying the allocation to study treatment and study eye as well as the assignment of subjects to the respective analysis cohorts.

For the Total Set, a listing will be provided by summarizing study termination/completion information, date of informed consent (from eCRF page 'Informed Consent'), unmasking information and treatment day of study termination/completion.

10.2 Protocol Deviations

The number of subjects who had at least one major as well as minor protocol deviation and all categories of Protocol Deviations will be summarized by counts (n) and percentages (%) for the SAF. Percentages will be calculated based on the number of subjects in the SAF.

A listing presents all Protocol Deviation data for the SAF.

10.3 Inclusion and Exclusion Criteria

Two listings will be provided for all subjects in the SAF displaying status of violated Inclusion and Exclusion criteria, respectively.

10.4 Demographic and Other Baseline Characteristics

10.4.1 Demographic and other Background Information

Age at Screening Visit (years), Ethnicity ('Japanese', 'Non-Japanese'), BMI (kg/m²) and number of alcohol units will be summarized per treatment group and overall by summary statistics or absolute counts (n) and percentages (%) for the SAF.

All demographic data, body weight and height at Screening as well as other background information will be listed for the SAF.

10.4.2 Medical History and Other Medical Conditions

The selected study eye will be summarized per treatment group and overall by absolute counts (n) and percentages based on the SAF.

Medical History will be summarized per treatment group and overall by absolute counts (n) and percentages (%) for the number of subjects with at least one medical history event for the SAF. Percentages will be calculated based on the number of subjects in the population.

A listing will present all reported, derived and coded medical history data based on the SAF.

In addition, all data recorded and derived for Schirmer's tear test, pregnancy tests and serology assessments (HB_sAg, HCV, HIV1/2) will be listed for the SAF.

10.4.3 Prior/Concomitant Medications

Prior and Concomitant medications will be summarized by treatment group and overall for the SAF separately on a per-subject basis (i.e. if a subject reported the same medications repeatedly the medications will be counted only once at the specific level of display). Absolute counts (n) and percentages (%) will be presented for the number of subjects taking at least one medication and per WHO Drug class 2 (ATC therapeutic main class) and per WHO Drug Name (Preferred Term) within ATC Drug class 2. Percentages will be calculated based on the number of subjects in the SAF.

A Listing will present all documented medication data for the SAF and will include a flag for Prior medication.

10.5 Exposure and Compliance to Study Medication

For exposure, the variables Individual Study Duration, Number of Drops Single Dose Scheme in Study Eye/Non-Study Eye, Number of Drops Multiple Dose Scheme in Study Eye/Non-Study Eye will be summarized for the SAF per treatment group.

For compliance, the proportions of 100% compliant subjects in the SAF for the single dose as well as the multiple dose scheme will be summarized by treatment group separately for study eye and non-study Eye by absolute counts (n) and percentages (%).

A listing will present for all SAF subjects all records documented on the eCRF Page “Administration of Study Drug” as well as the corresponding derived parameters.

10.6 Analysis of Primary Safety and Tolerability Assessments

10.6.1 Primary and Secondary Safety Endpoints – Adverse Events

The incidences of the primary and secondary endpoints TEAEs, TEAEs Single Dose, TEAEs Multiple Dose, FUAEs, Ocular TEAEs in Study Eye, Ocular TEAEs in Non-Study Eye will be presented for the SAF by study treatment and overall displaying the number of events as well as the number and percentages of subjects with at least one event.

In addition a general overview will be provided for AEs, non TEAEs, TEAEs during Treatment Period, TEAEs leading to premature withdrawal of the study treatment. TEAEs leading to study discontinuation, serious TEAEs, Fatal TEAEs, treatment related TEAEs, treatment related serious TEAEs, Ocular TEAEs, TEAEs of special interest and Mild, Moderate and Severe TEAEs will be given by study treatment and overall for subjects in the SAF. For each event, the number and percentages of subjects with at least one event as well as the total number of events will be displayed.

Detailed adverse event descriptive tables on will be summarized separately for each study treatment and overall for the following events:

- TEAEs
- TEAEs Single Dose
- TEAEs Multiple Dose
- FUAEs
- Ocular TEAEs
- Ocular TEAEs in Study Eye
- Ocular TEAEs in Non-Study Eye
- TEAEs by severity.
- Treatment related TEAEs.
- Serious TEAEs (only if reported).
- Treatment related serious TEAEs (only if reported)
- TEAEs leading to premature withdrawal of the Study Treatment.
- TEAEs leading to study discontinuation.

They will be summarized on a per-subject basis (i.e. if a subject reported the same event repeatedly the event will be counted only once at the specific level of display). Absolute counts (n) and percentages (%) will be presented for the number of subjects with at least one AE, and per SOC and per PT within SOC, for the SAF. Percentages will be based on the number of subjects in the population. In addition number of events will be provided.

Descriptive tables will be ordered by descending frequency of the overall number of subjects within each SOC regardless of treatment group, and then ordered within each SOC by the overall number of subjects within each PT regardless of treatment group. In the event of equal frequencies tables will be ordered by active treatment frequency and then alphabetically.

Listings will present all Adverse Event data for the SAF by subject.

In addition specific listings will be created for:

- Ocular TEAEs
- TEAEs leading to premature withdrawal of study treatment
- TEAEs leading to study treatment interruption
- TEAEs related to study treatment
- Serious AEs (only if reported)
- Serious TEAEs related to study treatment (only if reported)
- Fatal AEs (only if reported)

